## 11.0 Human Subject Issues

### 11.1 Regulatory Compliance

The study protocol, questionnaires, and consent forms will be submitted to IRB for approval. All study personnel must complete training in the Protection of Human Subjects per NIH guidelines. The proposed study will require eligible patients without regard for gender or ethnicity. The patient must sign the consent to be eligible for the trial. The consent form will describe the purpose of the trial, the procedures to be followed, and the risks and benefits of participation. Copies of the signed consent forms will be given to the patient, and this fact will be documented in the patient's study record.

### 11.2 Risk to Human Subjects

#### 11.2.1 *Intravenous Fructose Challenge*

Fructose has been recommended as an intravenous energy source during parenteral nutrition for patients with hepatic disease, uncontrolled diabetes mellitus, and in the postoperative state. Fructose is metabolised in the liver where it causes increased lactate formation, high-energy-phosphate depletion, increased uric-acid formation, and inhibition of protein synthesis. This results in increased concentrations of blood-lactate and serum-uric-acid. In hepatic disease fructose infusion may theoretically lead to lactic acidosis.

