## 5. Intravenous Fructose Challenge with MRS Measures of Energy Homeostasis

IV fructose challenge with MRS measures of energy homeostasis will be performed in the morning after an overnight fast. For all subjects, a vein will be catheterized and a venous blood sample drawn for laboratory evaluation (uric acid, glucose, insulin, lipids, and free fatty acids). A slow infusion of isotonic sodium chloride solution will be started to maintain catheter patency. After baseline MR data sets are obtained, fructose (250 mg/kg of body weight) dissolved in 25 to 50 mL of isotonic sodium chloride solution will be infused rapidly (over 30-60 seconds) through the indwelling venous catheter; further spectra will be collected for 1 hour. The slow saline infusion will be continued until the end of the study. At that time, another venous blood sample will be collected for laboratory evaluation (uric acid, glucose, insulin, lipids, and free fatty acids).

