The patient will sign the consent at screening visit to obtain any tests and procedures needed to finalize eligibility after chart review and will undergo a history and physical examination to identify other abnormalities and contraindications for participation. Anthropomorphic assessments (body weight [kg], body height [m], body mass index [BMI], waist circumference [cm], hip circumference [cm] and waist-to-hip ratio; vital signs (systolic and diastolic blood pressure, heart rate, respiratory rate, body temperature); and general physical findings, including hepatosplenomegaly, peripheral manifestations of liver disease, ascites, wasting or fetor, will be collected and recorded. Use of anti-NASH, antidiabetic, statin and fibrate medications in the 90 days prior to the biopsy will be obtained and recorded. Laboratory test results that need to be recorded from chart review or obtained as part of screening visit 1 include hepatitis B (HBsAg) and hepatitis C (anti-HCV), antinuclear antibody (ANA), anti-smooth muscle antibody (ASMA), anti-mitochondrial antibody (AMA), ceruloplasmin (if patient is less than 40 years old), A1AT concentration, iron and transferrin saturation, immunoglobulins (IgA, IgG, IGM), fasting glucose, insulin, and free fatty acids; CBC (Hgb, WBC, platelets, MCV, hematocrit), prothrombin time and INR, complete metabolic panel (sodium, potassium, chloride, bicarbonate, calcium, phosphate, BUN, creatinine, uric acid, albumin, total protein), GGT and hepatic panel (ALT, AST, alkaline phosphatase, total bilirubin, direct bilirubin), fasting lipid profile (total cholesterol, triglyceride, LDL, HDL), and hemoglobin A1c (HbA1c). Frequency and amount of alcohol intake will be obtained. Women of childbearing potential must have a negative pregnancy test.

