#### 9.4. Visit Day 0:

Patients with suspected NAFLD, who have not had a biopsy in the prior 6 months, will have a standard of care liver biopsy followed by co-localization of liver biopsy with MR.

Patients will be escorted to the Department of Radiology for baseline MRI/MRS imaging (MRI study protocol and data acquisition sequences detailed in [Appendix A](#)). Time 0 uric acid, insulin, glucose, lipid panel, and free fatty acids will be obtained. IV Fructose will be administered via heplock and dynamic measures of hepatic ATP and other metabolite measures will be obtained over 1 hour. At that time, another venous blood sample will be collected for laboratory evaluation (uric acid, glucose, insulin, lipids, and free fatty acids).

After acquisition of these late hepatic recover ATP measures, for the patients who have not had a historical biopsy in the 6 months prior to screening, a percutaneous liver biopsy will be performed as standard of care. After standard of care procedures and recovery are completed for the percutaneous liver biopsy, a very limited MRI will be performed to co-localize the site of liver biopsy with the exact site of MRI for modeling of non-invasive MRI biomarkers to features of chronic liver disease as characterized on liver biopsy. Subjects with suspected NAFLD may have two MRI's (one for IV fructose challenge and one for co-localization with liver biopsy site). For subjects with NAFLD, study participation will end after completion of the second MRI.

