#### 9.5 Adverse event reporting and Data Safety Monitoring

The investigators and staff will monitor and report adverse events to ensure patient safety. Any unanticipated or adverse events will be reported to IRB and NIH (Sponsor) in compliance with government regulations of event reporting in research studies. [name] [name], Chief of the Division of Gastroenterology and researcher with prior experience in the conduct of IV fructose challenge and MRS will serve as a data-safety monitor if any adverse events arise in the context of this study.

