### 9.5.2. Monitoring for adverse events

Adverse events will be recorded on study data forms whether or not they are thought to be associated with the study. Adverse events may be discovered during regularly scheduled visits or through unscheduled patient contacts between visits. Summary data on adverse events will be promptly assessed by investigators if they occur. Analyses or listings of adverse events will not be provided to the IRBs; however, adverse events involving unanticipated problems involving risks to participants, or breaches of protocol which might entail risk to participants will be reported to the IRB as soon as possible after they are discovered.

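### Minor safety improvement: section 11.2.1 names lactic acidosis as a theoretical risk of IV fructose in hepatic disease, but no scheduled challenge-day test includes lactate or bicarbonate

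*Combined protocol and SAP*

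**What the plan says.** Section 11.2.1 lists the metabolic effects of IV fructose, including higher blood lactate and higher serum uric acid, and closes with the warning: "In hepatic disease fructose infusion may theoretically lead to lactic acidosis". It opens on a different note: IV fructose has been recommended as an energy source for several groups, patients with liver disease among them.

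Section 5 gives the exposure as "fructose (250 mg/kg of body weight) dissolved in 25 to 50 mL of isotonic sodium chloride solution", pushed in over 30 to 60 seconds, with spectra then collected for an hour. Blood is drawn from all subjects beforehand. At the end, "another venous blood sample will be collected for laboratory evaluation (uric acid, glucose, insulin, lipids, and free fatty acids". Section 9.4 repeats this for the patient visit: "Time 0 uric acid, insulin, glucose, lipid panel, and free fatty acids will be obtained", with the same five items again at one hour.

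Bicarbonate appears once, in section 9.2, inside a metabolic panel introduced as "Laboratory test results that need to be recorded from chart review or obtained as part of screening visit 1".

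On safety oversight, section 9.5 has the investigators and staff monitor and report adverse events, and the designated person "will serve as a data-safety monitor if any adverse events arise in the context of this study". Section 9.5.2 says: "Adverse events may be discovered during regularly scheduled visits or through unscheduled patient contacts between visits". Section 9.4 adds: "For subjects with NAFLD, study participation will end after completion of the second MRI".

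**The concern.** The protocol names two blood changes that it expects from the challenge. It measures one of them, uric acid, on both sides of the infusion and does not measure the other, lactate, at all. The acidosis warning is directed at liver disease, which is the condition of the 70 planned NAFLD participants, and section 8.2 admits NASH-related cirrhosis.

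The hazard that the protocol itself raises is therefore left to clinical signs, although blood is already being taken at the two useful moments. The study would also end with no acid-base data on how NAFLD patients tolerate the challenge. That is a gap in safety information. It is not a failure against the stated objectives, which do not include acid-base tolerance.

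**Working it through.** The plan gives no figure to reproduce, and alpha, power and effect size play no part. The check sets the named risk against every place where a test or safeguard could answer it.

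| Place in the plan | What it provides | Lactate | Bicarbonate |
|---|---|---|---|
| Section 9.2, screening | Metabolic panel, possibly from chart review | no | yes |
| Sections 5 and 9.4, before infusion | Urate, glucose, insulin, lipids, fatty acids | no | no |
| Sections 5 and 9.4, about 60 minutes | The same five items | no | no |
| Section 3.1, aim b, 4 and 24 hours | Times only, no analyte; section 9.4 schedules no draw then | no | no |
| Sections 4.1 and Appendix A, MR | Phosphorus metabolites, water and fat in the liver | no | no |

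So 0 of the 2 challenge-day panels contain either analyte, 0 listed panels contain lactate, and 1 contains bicarbonate.

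**The screening value does not fill the gap.** It predates the infusion. Section 9.1 limits screening visits to a maximum of 8 weeks, but section 9.2 sets no limit on how old a chart-review result may be.

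**What lowers the risk.** Section 8.3 excludes hepatic decompensation (by albumin, INR, direct bilirubin or clinical history), creatinine of 2.0 mg/dL or greater, HbA1c of 9.5% or higher, platelets below 90,000/mm³ and ALT above 300 U/L. Eligible cirrhosis is therefore compensated. These criteria make acidosis less likely; they do not detect it.

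**What would catch an event.** Participants are on site for the hour of spectra, and those biopsied that day also have a recovery period. Symptoms would probably be noticed and reported. The data-safety monitor's role starts once an adverse event has arisen, so a change that nobody sees does not reach that person.

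**Exposure.** Dose = 0.25 g/kg × weight. The documents give no weights. At assumed weights of 70, 100 and 130 kg:
- 0.25 × 70 = 17.5 g
- 0.25 × 100 = 25 g
- 0.25 × 130 = 32.5 g

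**Size of the remedy.** Samples = participants × 2 draws; results = samples × 2 assays.
- NAFLD, n = 70: 70 × 2 = 140 samples; 140 × 2 = 280 results
- Controls, n = 30: 30 × 2 = 60 samples; 60 × 2 = 120 results
- Both groups: 200 samples and 400 results
- NAFLD with the 67 patients of section 10.4: 67 × 2 = 134 samples; 134 × 2 = 268 results

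These counts measure the work of the change, not the amount of harm avoided.

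**The case against.** The best defence is that this is a preference and not a defect. The warning in section 11.2.1 is hedged and gives no dose, and it follows a statement that IV fructose has been recommended in liver disease. The challenge is a single bolus. Sections 2.3 and 2.4 cite earlier IV fructose challenges in patients with liver disease. Staff have a general duty to monitor, venous access stays open through the hour, and a clinician may order lactate at any time. Most of this stands, and it is why the point is minor. The cited challenges settle nothing either way, because the documents report no safety results from them.

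A reader might infer that a symptom-free acidosis would go undetected. The documents do not support that: what is missing is a scheduled test, and staff may still test on clinical judgement. What remains true is that a patient without symptoms gives them little reason to do so.

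A reader might also infer that the dose is unsafe in cirrhosis. The documents give no rate of acidosis at this dose or any other, and they do not show that a symptom-free change would harm anyone.

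The remedy has limits too. The proposed trigger has no source in the documents, and one value at 60 minutes may miss a later peak.

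**Conclusion.** The point holds as a cheap safety improvement of minor weight. That lactate and bicarbonate are absent from the challenge-day panels is certain from the text. The clinical value of adding them is a judgement: the risk is theoretical, is reduced by the exclusions and by on-site observation, and cannot be quantified from the documents, so no rate is assumed here. Nothing in the sample size, the power statement or the primary comparison depends on it.

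The conclusion assumes that the listed panels are complete, so that lactate or bicarbonate is not measured under some unlisted local routine.

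**What to change.** Add lactate and serum bicarbonate to the time 0 and 60-minute samples in NAFLD participants. Preferably do the same in the 30 controls: section 5 already draws their blood and section 9.1 uses their data as reference, so an expected lactate rise could be told apart from an unusual one.

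Agree a trigger beforehand with the data-safety monitor of section 9.5. Lactate is expected to rise, so it should not trigger action alone. A workable default is a 60-minute lactate above the local laboratory's upper limit together with a bicarbonate below its lower limit and below the time 0 value. The investigator reviews results the same day, and a crossed trigger leads to clinical follow-up or a repeat sample. The standard-of-care biopsy need not wait unless the investigator so decides. Report the values descriptively as safety data.

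The cost is two assays at two existing draws and a short amendment, with no extra visit. The downsides are lactate sample handling, possibly an extra tube (the documents do not describe tube type or volume), and same-day turnaround. If results were required before biopsy or discharge, every NAFLD participant would have to wait. Because a single 60-minute value can miss a later peak, the gap is narrowed and not closed.

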#### 11.2.2 *MRI/MRS*

Standard safety precautions: screening; exclusion of potential participants with contraindications to MR. MR is a minimal risk procedure if standard precautions and practice exercised. Standard precautions for MR procedures include: claustrophobia, anxiety, discomfort from lying supine for 30-60 minutes, hearing loss, and heating of metal in the body. Patients with metal will be screened by questionnaire and excluded when the presence of metal is known or suspected. Sources include the presence of a cardiac pacemaker or defibrillator; metal fragments in eyes, skin, body; heart valve replacement, brain clips, venous umbrella; being a sheet-metal worker or welder; aneurysm surgery, intracranial bypass, renal, aortic clips; prosthetic devices such as middle ear, eye, joint or penile implants, joint replacements; hearing aid, neurostimulator,

insulin pump; intrauterine device; shunts/stents, metal mesh/coil implants; metal plate/pin/screws/wires, or any other metal implants; permanent eyeliner, eyebrows.

### ***11.2.3. Patient privacy***

It is the investigator's responsibility to conduct the protocol under the current version of Declaration of Helsinki, Good Clinical Practice, and rules of local IRBs. The investigator must ensure that the patient's anonymity be maintained during all aspects of their study participation. Patients will be identified only by an identification code but not by their name, SSN, or hospital medical record number. All laboratory specimens, study forms, reports, and other records that are part of the study data collection materials will be identified by coded number to maintain patient confidentiality. All records will be kept in locked office. All electronic records of study data will be identified by coded number. Clinical information will not be released without written permission of the patient, except as necessary for monitoring by the IRB. Consent procedures and forms, and the communication, transmission and storage of patient data will comply with individual site IRB and NIH requirements for compliance with The Health Insurance Portability and Accountability Act (HIPAA). Investigators will maintain a separate confidential enrollment log which matches identifying codes with the patients' names and addresses (i.e., available only to local clinic staff). All study material will be maintained in strict confidence.

### ***11.2.5 Sample Biobanking***

It is anticipated that serum, plasma, DNA, and liver tissue from the participants will be stored for future studies related to NASH and possibly other liver/metabolic diseases in our Duke NAFLD Clinical Database and Biorepository. These samples will be stored in a central repository. Specific IRB approval will be as per specific institutional guidelines addressing the issues such as (a) obtaining a separate informed consent, (b) storage, (c) transportation of the material, (d) who will have access to the material, and (e) what investigations will be conducted.

## Appendix A:

### **MRI/MRS Protocols for Assessment of Energy Homeostasis and MR Biomarkers for NAFLD**

In all cases no patient repositioning will need to occur between data acquisitions for different MR nuclei. Primary measures are indicated in blue and include  $^1\text{H}$  MRI/MRS for water and fat measures and  $^{31}\text{P}$  UTE MRS for fructose measures. In all cases, the multiple acquisitions acquired prior to the injection of fructose will serve as test-retest cases for confirming measurement variance in the presence of pathology. Interleaved measures for experimental hypotheses may be moved or removed in order to ensure sufficient primary measures within the allotted MR time slot.

Only MR Slot 1 and Slot 2 protocols shown below will be used on the healthy volunteers for Aim 1 in order to optimize these protocols. The full MR protocol shown below will be performed for NAFLD subjects.

MR Slot 1 (Time 0)	MR Slot 2 (Post biopsy)
<math>^1\text{H}</math> MRI - anatomical $^1\text{H}$ MRI/MRS – water/fat $^{31}\text{P}$ UTE MRS – fructose baseline (multiple acquire) Fructose injection $^{31}\text{P}$ UTE MRS – fructose dynamic (multiple acquire) $^1\text{H}$ EPSI – water/fat $^{31}\text{P}$ UTE MRS – fructose dynamic (multiple acquire)	<math>^1\text{H}</math> MRI - anatomical for biopsy localization $^{31}\text{P}$ UTE MRS – fructose recovery (multiple acquire) $^1\text{H}$ MRI/MRS – water/fat

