## 2.5 Use of MRI/ MRS as a Non-invasive Biomarker of NAFLD

Various MRI/MRS methods are used to investigate liver status (42-45). Tools used in this study will be extensions of these methods validated in other organs, and that we have adapted for use in the torso. All spectroscopy tools will use localized techniques, to provide volumetric hepatic metabolite measures. Hepatic energy homeostasis (ATP values) will be measured using an ultra-short TE sequence with “echo times” as short as 70  $\mu$ s, which increases the signal to noise ratio allowing shorter temporal sampling if needed. Hepatic lipid and water signals will be measured within a breath hold using  $^1\text{H}$  MRI sequences .

We will adapt the MRS acquisitions to provide a known reference against which to calibrate hepatic metabolite values. By calibrating the metabolites values, we will know exactly which metabolite(s) change and by how much, both within our cohort and in response to our dietary intervention study.

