## 3. Study design

### 3.1 Design overview

The proposed open label study is single-center randomized, phase II clinical trial designed to address the following specific aims:

- a) **To optimize an MR protocol to characterize the range and rates of *baseline and dynamic* measures of metabolism and energy homeostasis following an acute IV fructose challenge.** Volumetric and quantitative measures of hepatic lipid deposition, energy levels, and water homeostasis will be characterized in normal volunteers to determine typical ranges and coefficients of variation for each technique.
- b) **To differentiate the baseline and dynamic changes of metabolic and energy homeostasis following an acute IV fructose challenge in patients with biopsy-proven NAFLD.** MR-based measurements from the Aim 1 protocol will be correlated to clinical measures of metabolism, energy homeostasis and histologic disease activity before, during and at 4 and 24 hours following IV fructose challenge in regions co-localized and distant from biopsy.

A cohort study of healthy volunteers (n=30) and patients with NAFLD (n=70) will be enrolled. Healthy volunteers will have no evidence of chronic liver disease (normal liver enzymes and normal liver imaging and/or a liver biopsy performed for clinical evaluation of liver disease but whose pathology results note no pathologic abnormalities). Patients with suspected NAFLD who will undergo a standard-of-care liver biopsy, or who have had a historical biopsy within 6

months of the Screening visit, will have both acute intravenous fructose challenge for assessing baseline and post-dietary intervention *static and dynamic* measures of metabolism and energy homeostasis. Co-localization of liver biopsy with MRI to optimize / assess MRI measures of the histologic features of NAFLD will be performed to develop MRI as a surrogate “biomarker” for liver biopsy. With the exception of the liver biopsy, no accurate non-invasive biomarker for disease activity currently exists.

Screening for eligibility and collection of baseline data will span up to 8 weeks. Patients who have had a liver biopsy showing NAFLD within 6 months of the Screening visit or patients who will be undergoing a standard of care percutaneous liver biopsy for NAFLD will be consented.

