## 10. Statistical design and analysis

Coefficients of variance (CV) will be used to evaluate reproducibility of MRS/MRI baseline measures. Intra-class correlations (ICC) will be used to measure absolute test-retest baseline measure reliability for the test-retest subjects. ICCs will be calculated with a model that separates subject, voxel, measurement and error variances using an analysis of variance (ANOVA) method. We will include a number of multi-factorial random effects models (66, 67) which use a restricted maximum likelihood (REML) algorithm to prevent negative variance terms. The ANOVA model for metabolite estimates across all subjects will be  $M_{ijk} = \mu + S_i + V_{ij} + N_k + e_{ijk}$  where  $\mu$  is the average across all voxels,  $S_i$  = subject,  $V_{ij}$  = voxel and  $N_k$  = scan random effects, respectively and  $e_{ijk}$  is residual error. For ICC in individual subjects, we leave out the  $S_i$  term. ICCs for test-retest measures will be based on random-effects analysis of the variance models and will be computed as follows:  $ICC = \sigma^2_B / (\sigma^2_B + \sigma^2_w + \sigma^2_e)$  where  $\sigma^2_B$  is generalized between-subject variance of metabolites,  $\sigma^2_w$  is within-subject variance between scans 1 and 2 and  $\sigma^2_e$  is variance due to random noise (68). CVs for test-retest reproducibility will be calculated using  $CV = \sqrt{\sigma^2_w + \sigma^2_e} / \mu$ . Similarly we will obtain CVs from the first 20 subjects in Aim2 and will compare these to the normal population.

Dynamic changes will be characterized in a more *ad hoc* manner. From the metabolite estimates at time  $t$  ( $M_{ijkt}$ ), the following parameters will be measured for each individual (subscript  $i$ ): baseline ( $B_i$  = mean of  $M_{jkt}$ , where  $t$  = prior to fructose challenge), range of change from baseline ( $D_i = B_i - \min(M_{jkt})$  if any), time to maximal change ( $T_i$  = time to reach  $\min(M_{ijkt})$ ), time to baseline recovery ( $R_i$ , if applicable). A 95% confidence interval of baseline will be used to test if the metabolite level is recovered to the baseline. If it does not reach the baseline, we will estimate the baseline based on the assumption of a linear recovery rate. Since metabolite levels will be measured at discrete time points, spline smoothing will be used to fit the curve. These values will be averaged across the cohort of volunteers and simple measures of variance calculated.

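### Appendix A schedules no pre-fructose repeat of the 1H water/fat measure, so the baseline coefficient of variation promised for lipid and water has no clean retest data behind it

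*Combined protocol and SAP*

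**What the plan says.** **What is promised.** Aim (a) in section 3.1 covers three quantities: hepatic lipid, energy and water. It says that they "will be characterized in normal volunteers to determine typical ranges and coefficients of variation for each technique". Section 10 opens with "Coefficients of variance (CV) will be used to evaluate reproducibility of MRS/MRI baseline measures" and excludes no nucleus. Intra-class correlations (ICCs) are promised more narrowly. They "will be used to measure absolute test-retest baseline measure reliability for the test-retest subjects", and neither the membership nor the size of that group is given anywhere. Section 10 also plans to obtain CVs from the first 20 Aim 2 patients and compare them with the normal population.

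**Where the retest data come from.** Appendix A names two primary measures, 1H MRI/MRS for water and fat and 31P UTE MRS. It then states, as a rule without exceptions, that "the multiple acquisitions acquired prior to the injection of fructose will serve as test-retest cases for confirming measurement variance in the presence of pathology".

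**What is scheduled.** In the Slot 1 column the 31P line before the injection reads "fructose baseline (multiple acquire)". The 1H MRI/MRS water/fat line appears once before the injection and has no such tag. 1H EPSI appears only after the injection. The 1H MRI/MRS water/fat line returns in Slot 2, whose heading places it after the biopsy. Appendix A applies both slots to healthy volunteers and the complete protocol to NAFLD subjects. Section 9.4 describes the second MRI as much reduced in scope and attaches it to patients biopsied on study. Section 9.1 lists no separate retest session for controls.

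**The concern.** A CV for test-retest reproducibility needs at least two like-for-like acquisitions per person under the same conditions. For 31P the plan has them. For fat and water the only source that Appendix A names seems to hold one acquisition, although aim (a) promises a CV for these quantities too.

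An analyst following the plan would then either report no reproducibility for lipid and water, or use Slot 1 against Slot 2 as the retest pair. The second choice counts any real change after fructose as measurement error. That matters here because section 3.6 makes water homeostasis a dynamic outcome in its own right. It would also affect the planned comparison of CVs between patients and controls: patients would carry a biopsy between the two scans and controls would not, so a difference in CV could reflect the procedure rather than the disease.

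**Working it through.** The documents give no target CV, number of repeats or precision for reproducibility, so there is no stated figure to reproduce. The check is a count of acquisitions followed by the section 10 formulas.

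**Inputs from the documents**
- 30 controls and 70 NAFLD patients (section 3.4); patient CVs from the first 20 (section 10).
- Section 10 model: M_ijk = μ + S_i + V_ij + N_k + e_ijk, with subject, voxel and scan effects.
- Section 10: CV = √(σ²_w + σ²_e)/μ, where σ²_w is the variance within a person across a first and a second scan.

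**Count of 1H MRI/MRS water/fat acquisitions per person, as listed**

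| Period | Acquisitions | Comment |
|---|---|---|
| Slot 1, before fructose | 1 | no repeat tag |
| Slot 1, after fructose | 0 | EPSI only, a different sequence |
| Slot 2 | 1 | after fructose; after biopsy in patients |

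**Step 1: pre-fructose data only.** With k acquisitions per person, retest degrees of freedom are n(k − 1). For k = 1 this is 0 whether n is 20, 30 or 70. The scan effect N_k has one level and merges with μ. If there are several voxels, V_ij and e_ijk appear only as a sum, so spread across voxels measures spatial variation in the liver and not scan-to-scan error.

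**Step 2: Slot 1 against Slot 2.** Here k = 2, giving 30 × (2 − 1) = 30 df in controls and at most 20 × (2 − 1) = 20 df in the first 20 patients, if all of them have Slot 2. A variance can be computed. Its content is the difficulty. With true CV c and mean shift m between slots (as a fraction of the mean), and the shift not removed, the apparent CV is √(c² + m²/2). Taking c = 5% (assumed):
- m = 2%: √(0.0025 + 0.0002) = 5.2%
- m = 5%: √(0.0025 + 0.00125) = 6.1%
- m = 10%: √(0.0025 + 0.005) = 8.7%

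If the mean shift is removed but the true change varies between people with SD t, the same form applies with t in place of m: t = 5% gives 6.1% and t = 10% gives 8.7%. None of c, m and t is in the documents.

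**Step 3: one added pre-fructose repeat.** The 95% limits for the within-subject SD, as multiples of the estimate, are √(df/χ²₀.₉₇₅) and √(df/χ²₀.₀₂₅):
- 30 controls, df 30: √(30/46.98) = 0.80 and √(30/16.79) = 1.34
- first 20 patients, df 20: √(20/34.17) = 0.77 and √(20/9.59) = 1.44

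This takes one value per person per acquisition and no systematic shift between two back-to-back acquisitions. The limits carry over approximately to the CV.

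**The case against.** The strongest reply has four parts.

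1. **The table may not be a count.** It is a sequence list, and a missing tag does not strictly rule out a repeat. This stands as a caution. Even so, every 31P line carries the tag and no 1H line does, so a single acquisition is the natural reading.

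2. **Appendix A may not be the only retest source.** Its sentence speaks of pathology, which suggests a confirmatory check in patients, while section 10 refers separately to test-retest subjects. That group is never defined, however, and section 9.1 gives controls no extra session in which a retest could occur. The reply points to a further gap and does not supply the missing data.

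3. **Slot 2 supplies a second scan.** This is correct. A reader might infer that reproducibility of fat and water cannot be estimated at all. The documents do not support that, because the Slot 2 listing makes a scan variance computable and section 10 speaks of two scans. What is missing is a baseline retest free of fructose. Nor does the biopsy objection reach controls, who have no study biopsy; for them only the fructose objection is documented.

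4. **Back-to-back repeats omit repositioning.** A same-session pair shows within-session repeatability only, and use of a biomarker across visits would include repositioning. This also stands, and the result should be labelled accordingly.

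A reader might also infer that the plan promises both CVs and ICCs for every measure. It does not: the promise for each technique is of CVs, and ICCs are confined to the undefined test-retest group.

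**Conclusion.** The point holds in a limited form. As Appendix A is listed, the retest source it names gives 0 degrees of freedom for the primary 1H water/fat measure, and the only like-for-like repeat is confounded with fructose in everyone who has it and also with biopsy in patients. A clean baseline CV for lipid and water, which aim (a) promises, is therefore not supported.

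The conclusion rests on reading the untagged 1H line as one acquisition. The size of any bias is unknown. The rise from 5% to between 5.2% and 8.7% is illustrative and depends wholly on assumed values; with no true change between slots there would be no inflation.

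A reader might infer that the main results are undermined. The documents do not support that. The principal objective in section 1.2 concerns hepatic ATP, for which repeated 31P baselines are scheduled, and the comparison of MR measures with histology does not depend on this CV. The gap is nevertheless worth closing before scanning, because a pre-fructose repeat cannot be recovered afterwards.

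**What to change.** - In Slot 1 of Appendix A, list the 1H MRI/MRS water/fat acquisition twice before the fructose injection, with the same sequence and prescription, at least in the 30 controls and the first 20 NAFLD patients.
- In section 10, define these participants as the test-retest subjects. Compute the CV and ICC for fat and water from that pair, and label the result within-session repeatability.
- State that Slot 2 1H data are not used as the baseline retest.
- Reconcile section 9.4 with Appendix A on which NAFLD patients have the second MRI and what it contains.
- If the repeat cannot be fitted in, restrict the reproducibility claim in aim (a) and section 10 to 31P, and state that 1H reproducibility is not assessed.

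The cost is small. Section 2.5 says "Hepatic lipid and water signals will be measured within a breath hold", so the repeat adds about one breath-hold to a session already planned, or a few minutes of scanner time if the MRS part is repeated as well. Appendix A already allows interleaved experimental measures to be moved or dropped to protect the primary ones. No added visit is needed.
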